## 9.4. Statistical Analyses

The SAP will be developed and finalized before database lock for the final analysis. The SAP will describe the participant populations to be included in the analyses, and procedures for accounting for missing, unused, and spurious data. This section is a summary of the planned statistical analyses of the primary, secondary, CCI [REDACTED] endpoints.

All CIs in the statistical analysis will be calculated as 2-sided at the 95% level.

### 9.4.1. Immunogenicity Analyses

The statistical analysis of immunogenicity results will be primarily based on the evaluable 13-matched immunogenicity and evaluable 7-additional immunogenicity populations (primary immunogenicity population) as defined in Section 9.3.

CCI [REDACTED]

Participants will be summarized according to the vaccine group to which they are randomized for analysis based on immunogenicity populations. Missing serology data will not be imputed. Titers below LLOQ or denoted as BLQ will be set to  $0.5 \times \text{LLOQ}$  for analysis.

Endpoint	Statistical Analysis Methods
Primary immunogenicity	
 
GMRs of pneumococcal serotype-specific OPA titers 1 month after vaccination 
 
(1) For each of the 13 matched serotypes, the ratio of the GMT 1 month after 20vPnC in the 20vPnC/saline group to the GMT 1 month after 13vPnC in the 13vPnC/PPSV23 group (Visit 2) will be provided;
 
(2) For each of the 7 additional serotypes, the ratio of the GMT 1 month after 20vPnC in the 20vPnC/saline group (Visit 2) to the GMT 1 month after PPSV23 in the 13vPnC/PPSV23 group (Visit 3) will be provided.
 
 
 

Endpoint	Statistical Analysis Methods
	
As the primary approach to calculate the GMR and CI for each serotype for OPA titer, a linear regression model that includes terms for age, corresponding baseline OPA titer, sex, smoking status, country, and vaccine group will be used to calculate the serotype-specific OPA GMR and 2-sided 95% CI, along with the model-based least squares GMTs and associated 2-sided 95% CIs, for each vaccine group. CCI
 
[REDACTED]
 
[REDACTED]
 
Hypothesis testing for NI of 20vPnC to the control vaccine (13vPnC for the 13 matched serotypes or PPSV23 for the 7 additional serotypes) will be performed as described in Section 9.1.2.1.

Secondary immunogenicity	
 
• GMTs of pneumococcal serotype-specific OPA titers 1 month after vaccination
 
 
OPA GMTs at 1 month after 20vPnC for the 20vPnC/saline vaccine group and 13vPnC (Visit 2) for the 13vPnC/PPSV23 vaccine group will be summarized for the 13 matched serotypes in each vaccine group. For the 7 additional serotypes, the GMTs at 1 month after 20vPnC (Visit 2) for the 20vPnC/saline vaccine group and the GMTs at 1 month after PPSV23 (Visit 3) for the 13vPnC/PPSV23 vaccine group will be summarized.
 
GMTs and the associated 2-sided 95% CIs will be derived by calculating means and CIs on the natural log scale based on Student's t-distribution, and then exponentiating the results.
 
 
• GMFRs of pneumococcal serotype-specific OPA titers
 
 
OPA GMFRs from before vaccination (Visit 1) to 1 month after 20vPnC or 13vPnC (Visit 2) for the 13 matched serotypes in each vaccine group will be summarized. For the 7 additional serotypes, the GMFRs from before vaccination (Visit 1) to 1 month after 20vPnC (Visit 2) for the 20vPnC/saline vaccine group and the GMFRs from before vaccination (Visit 1) to 1 month after PPSV23 (Visit 3) for the 13vPnC/PPSV23 vaccine group will be summarized. GMFRs will be limited to participants with nonmissing values both before any vaccination and after the indicated vaccination.
 
The GMFR for each serotype will be calculated as the mean of the difference of logarithmically transformed assay results (later time point – earlier time point) and transformed back to the original scale. Two-sided 95% CIs will be obtained by calculating CIs using Student's t-distribution for the mean difference of the

[figure not shown]
Endpoint	Statistical Analysis Methods
	
logarithmically transformed assay results and transforming the limits back to the original scale.
 
 
Percentage of participants with a <math>\geq 4</math>-fold rise in pneumococcal serotype-specific OPA titers Percentage of participants with a <math>\geq 4</math>-fold rise in serotype-specific OPA titer from before vaccination (Visit 1) to 1 month after 20vPnC or 13vPnC (Visit 2) for the 13 matched serotypes in each vaccine group will be summarized. For 7 additional serotypes, the percentage of participants with a <math>\geq 4</math>-fold rise in serotype-specific OPA titer from before vaccination (Visit 1) to 1 month after PPSV23 (Visit 3) for the 13vPnC/PPSV23 vaccine group will be summarized. The percentage of participants with a <math>\geq 4</math>-fold rise in serotype-specific OPA titer will be limited to participants with nonmissing values both before any vaccination and after the indicated vaccination. The associated 2-sided CIs will be obtained using the Clopper-Pearson method.
 
Percentage of participants with pneumococcal serotype-specific OPA titers <math>\geq</math> LLOQ Percentage of participants with OPA titers <math>\geq</math> LLOQ will be provided for time points (same as <math>\geq 4</math>-fold rise) and serotypes. The associated 2-sided CIs will be obtained using the Clopper-Pearson method.
 

[REDACTED]	[REDACTED]

#### 9.4.2. Safety Analyses

Endpoint	Statistical Analysis Methods
Primary	
 
Descriptive statistics will be provided for each reactogenicity endpoint for each vaccine group. Local reactions from Day 1 through Day 10 after vaccination and systemic events from Day 1 through Day 7 after vaccination will be presented by severity cumulatively across severity levels. Descriptive summary statistics will include counts and percentages of participants with the indicated endpoint and the associated Clopper-Pearson 2-sided 95% CIs. Between-group differences (20vPnC/saline [Vaccination 1] - 13vPnC/PPSV23 [Vaccination 1]) in percentage and 2-sided 95% CIs will be provided. The Miettinen and Nurminen method will be used to derive the 2-sided 95% CI for the difference in percentages between vaccine groups.
 

Endpoint	Statistical Analysis Methods
	
In addition, descriptive summaries for each reactogenicity endpoint after each vaccination for each vaccine group and the associated 2-sided 95% Clopper-Pearson CIs for Japanese participants only will also be provided.
 
 
• AEs will be categorized according to MedDRA terms. A 3-tier approach will be used to summarize AEs. Under this approach AEs are classified into 1 of 3 tiers: (1) Tier 1 events are prespecified events of clinical importance and are identified in a list in the product's safety review plan; (2) Tier 2 events are those that are not Tier 1 but are considered "relatively common"; a MedDRA preferred term is defined as a Tier 2 event if there are at least 1% of participants in at least 1 vaccine group reporting the event; and (3) Tier 3 events are those that are neither Tier 1 nor Tier 2 events. For both Tier 1 and Tier 2 events, the 2-sided 95% CIs for the difference in percentage of participants reporting the events between groups will be calculated using the Miettinen and Nurminen method. In addition, for Tier 1 events, the asymptotic p-values will also be presented for the difference in percentage of participants reporting the events, based on the same test statistic and under the assumption that the test statistic is asymptotically normally distributed. There is no Tier 1 event identified for 20vPnC at this stage. Descriptive summary statistics (counts, percentages, and associated 2-sided Clopper-Pearson 95% CIs) will be provided for Tier 3 events for each vaccine group.
 
• SAEs will be categorized according to MedDRA terms. Counts, percentages, and the associated 2-sided Clopper-Pearson 95% CIs of SAEs will be provided for each vaccine group.
 
• The safety analyses are based on the safety population. Participants' data will be summarized by vaccine group according to the study interventions they actually received. Missing e-diary data will not be imputed; missing AE dates will be handled according to the Pfizer safety rules.
 

Secondary	
 
• For each reactogenicity endpoint, summaries (20vPnC/saline [Vaccination 1] and 13vPnC/PPSV23 [Vaccination 2]) and 2-sided 95% Clopper-Pearson CIs, for Japanese participants only, will be provided. The Miettinen and Nurminen method will be used to derive the 2-sided 95% CI for the difference in percentages between vaccine groups.
 

CCI

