### 2.3.1. Risk Assessment

Potential Risk of Clinical Significance	Summary of Data/Rationale for Risk	Mitigation Strategy
Study Intervention(s): 20vPnC, 13vPnC, and PPSV23		
The relevant key risks associated with 20vPnC and 13vPnC include local reactions (injection site pain, redness, and swelling); systemic events (fever, headache, fatigue, joint pain, and muscle pain); and allergic reactions, including skin rash, face or lip swelling, wheezing, shortness of breath, or severe allergic reaction (eg, anaphylactic shock).	The risks are based on the 20vPnC IB and the 13vPnC and PPSV23 package inserts.	
Eligibility criteria have been selected to ensure that only appropriate participants are included in the study (see Section 5).
 
E-diary and AE data will be monitored by the investigator (or designee) and sponsor.
 
Participants who develop exclusionary conditions during study conduct or participants with significant reactions after Visit 1 vaccination or AEs considered by the investigator to present increased risk to the participant if he/she received additional study vaccinations will be excluded from further vaccinations.
 
Sites with capabilities to manage potential immediate severe allergic reactions, including anaphylaxis, will be selected.

Study Procedures		
There is the risk of fainting, and pain, swelling, bruising, and infection at the venipuncture site.	Venipuncture is required to collect immunogenicity data from participants.	Only qualified nurses, physicians, nurse practitioners, physician assistants, phlebotomists, or medical assistants certified or otherwise authorized to draw blood per the standards and procedures of the investigative site, as allowed by institutional, local, and country guidance, will be allowed to draw blood to minimize local complications.

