To describe the immune responses to all 20 serotypes induced by 20vPnC.	In evaluable participants for each of the 20 serotypes: 
 
Serotype-specific OPA GMTs 1 month after vaccination* in each vaccine group
 
GMFRs in serotype-specific OPA titers from before to 1 month after vaccination* in each vaccine group
 
Percentage of participants with <math>\geq 4</math>-fold rise in serotype-specific OPA titers from before to 1 month after vaccination* in each vaccine group
 
Percentage of participants with serotype-specific OPA titers greater than or equal to the LLOQ 1 month after vaccination* in each vaccine group
 
	
 
Serotype-specific OPA titers
 

Secondary Safety	Secondary Safety	Secondary Safety
To describe the reactogenicity profile of PPSV23 following 13vPnC in Japanese participants (only for participants enrolled at Japan sites).	In participants receiving at least 1 dose of study intervention and having safety follow-up after vaccination from each vaccine group: 
 
The percentage of participants reporting prompted local reactions within 10 days after the second vaccination (PPSV23 or saline)
 
The percentage of participants reporting prompted systemic events within 7 days after the second vaccination (PPSV23 or saline)
 
	
 
Prompted local reactions (redness, swelling, and pain at the injection site)
 
Prompted systemic events (fever, headache, fatigue, muscle pain, and joint pain)
 

\* Note: "1 month after vaccination" refers to 1 month after vaccination with 20vPnC (20vPnC/saline group), or 1 month after vaccination with 13vPnC for the 13 matched serotypes or PPSV23 for the 7 additional serotypes (13vPnC/PPSV23 group).

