## **7. DISCONTINUATION OF STUDY INTERVENTION AND PARTICIPANT DISCONTINUATION/WITHDRAWAL**

### **7.1. Discontinuation of Study Intervention**

Participant eligibility must be confirmed prior to each vaccination in order to continue in the study.

If a participant no longer meets the eligibility criteria during the vaccination period of the study, further vaccinations should be discontinued, but the participant may remain in the study. If a participant is discontinued from vaccination and the participant consents, safety follow-up will be conducted as per [Section 8.3](#) (AEs and SAEs will be collected for 1 month after the last study vaccination).

In rare instances, it may be necessary for a participant to permanently discontinue study intervention (definitive discontinuation). Reasons for definitive discontinuation of study intervention include the following: the participant no longer meets eligibility criteria, specific protocol deviations, withdrawals by the participant, and certain AEs or SAEs.

Note that discontinuation of study intervention does not represent withdrawal from the study. If study intervention is definitively discontinued, the participant will remain in the study to be evaluated for safety. See the SoA for data to be collected at the time of discontinuation of study intervention and follow-up for any further evaluations that need to be completed.

In the event of discontinuation of study intervention, it must be documented on the appropriate CRF/in the medical records whether the participant is discontinuing further receipt of study intervention or also from study procedures, postvaccination study follow-up, and/or future collection of additional information.

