3.2. Secondary Endpoints

3.2.1. Secondary Safety Endpoint (Participants at Japan Sites Only)

The same summaries as specified in Sections 3.1.1.1 and 3.1.1.2 will be provided.

- Prompted local reactions (redness, swelling, and pain at the injection site) within 10 days after the second vaccination (PPSV23 following 13vPnC or saline following 20vPnC)
- Prompted systemic events (fever, headache, fatigue, muscle pain, and joint pain) within 7 days after the second vaccination (PPSV23 following 13vPnC or saline following 20vPnC)

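### The secondary safety row of Protocol 9.4.2 sets 20vPnC at Vaccination 1 against PPSV23 at Vaccination 2, but the estimand concerns the second vaccination in both groups

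*Protocol*

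**What the plan says.** The secondary safety objective is to describe how PPSV23 given after 13vPnC is tolerated at Japan sites. Protocol section 3 defines the estimand for local reactions, in each vaccine group, as "The percentage of participants reporting prompted local reactions within 10 days after the second vaccination (PPSV23 or saline"); the systemic-event estimand has the same form over 7 days. SAP 3.2.1 agrees, with the endpoint falling "within 10 days after the second vaccination (PPSV23 following 13vPnC or saline following 20vPnC").

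The Secondary row of Protocol 9.4.2 says instead that "summaries (20vPnC/saline [Vaccination 1] and 13vPnC/PPSV23 [Vaccination 2]) and 2-sided 95% Clopper-Pearson CIs, for Japanese participants only, will be provided". Its next sentence is: "The Miettinen and Nurminen method will be used to derive the 2-sided 95% CI for the difference in percentages between vaccine groups". The row names no other groups or time points.

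Three further places bear on the point:

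- The Primary row of the same table pairs like with like: "Between-group differences (20vPnC/saline [Vaccination 1] - 13vPnC/PPSV23 [Vaccination 1]) in percentage and 2-sided 95% CIs will be provided".
- The Primary row also promises, for Japanese participants, "descriptive summaries for each reactogenicity endpoint after each vaccination for each vaccine group", with Clopper-Pearson intervals and no between-group difference. SAP 5.2 likewise plans summaries after each vaccination by group.
- SAP 6.2.1.1 and 6.2.1.2 analyse PPSV23 or saline after the second vaccination. Their visible text gives percentages with Clopper-Pearson intervals and no difference, whereas SAP 6.1.1.1 and 6.1.1.2 state one explicitly for the first vaccination.

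**The concern.** In the 20vPnC/saline group, Vaccination 1 is 20vPnC and Vaccination 2 is saline. The row's label therefore replaces saline with an active vaccine in the only difference specified for this objective. No visible objective or estimand asks for 20vPnC dose 1 against PPSV23 dose 2.

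The saline injection at Vaccination 2 is a concurrent, participant-blinded control from the randomised design. It is what separates reactions to PPSV23 from background symptoms in adults aged 60 and over. The Vaccination 2 diary is collected at Japan sites because the Japanese regulator asked for more information on this schedule, so this is where that control is most useful.

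The contrast as written loses it in two ways:

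- **Timing.** The two injections are 28 to 42 days apart.
- **Selection on one side only.** Protocol 2.3.1 withholds further injections from "participants with significant reactions after Visit 1 vaccination or AEs considered by the investigator to present increased risk to the participant", and Protocol 7.1 adds: "If a participant no longer meets the eligibility criteria during the vaccination period of the study, further vaccinations should be discontinued". The PPSV23 rate comes from people who passed that filter; the 20vPnC dose 1 rate does not.

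**Working it through.** **1. The passages side by side**

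| Source | 20vPnC/saline group | 13vPnC/PPSV23 group | Difference stated? |
|---|---|---|---|
| Secondary safety estimand (Protocol 3; SAP Table 2) | Vaccination 2 (saline) | Vaccination 2 (PPSV23) | No, percentage per group |
| Protocol 9.4.2, Secondary row | Vaccination 1 (20vPnC) | Vaccination 2 (PPSV23) | Yes, Miettinen-Nurminen |
| Protocol 9.4.2, Primary row, Japan summaries | each vaccination | each vaccination | No |
| SAP 6.2.1.1 and 6.2.1.2, visible text | Vaccination 2 (saline) | Vaccination 2 (PPSV23) | No |

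The protocol has a difference on the wrong pair. The visible SAP has the right pair and no difference.

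**2. The size of the discrepancy, algebraically**

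Take the direction used in the Primary row, 20vPnC/saline minus 13vPnC/PPSV23. Let a be the 20vPnC rate at Vaccination 1, s the saline rate at Vaccination 2 and b the PPSV23 rate at Vaccination 2.

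- Row as written: a - b
- Vaccination 2 in both groups: s - b
- Discrepancy: (a - b) - (s - b) = a - s

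It is zero only when 20vPnC and saline give the same rate, as may hold for rare events.

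**3. Illustration**

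The documents contain no reaction rates and no figure to reproduce for this endpoint, so all rates below are assumptions.

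Inputs: about 700 participants in Japan (Protocol 9.2) at 1:1 gives 700/2 = 350 per group at Vaccination 1. Assuming 10% do not contribute at Vaccination 2 (borrowed from the protocol's nonevaluable rate) gives 350 × 0.9 = 315 per group.

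The Miettinen-Nurminen limits are the values d at which

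(p1 - p2 - d) / sqrt{ [r1(1 - r1)/n1 + r2(1 - r2)/n2] × N/(N - 1) } = ±1.96,

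where r1 and r2 are the maximum-likelihood rates constrained to r1 - r2 = d, and N = n1 + n2.

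| Assumed 20vPnC / PPSV23 / saline | Row as written, points (95% CI) | Vaccination 2 in both groups, points (95% CI) |
|---|---|---|
| 20 / 20 / 5% | 70/350 vs 63/315: 0.0 (-6.2 to 6.1) | 16/315 vs 63/315: -14.9 (-20.1 to -10.0) |
| 40 / 40 / 10% | 140/350 vs 126/315: 0.0 (-7.5 to 7.4) | 32/315 vs 126/315: -29.8 (-36.2 to -23.4) |
| 60 / 40 / 10% | 210/350 vs 126/315: +20.0 (12.4 to 27.3) | 32/315 vs 126/315: -29.8 (-36.2 to -23.4) |

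The 10% loss matters little. With 350 per group at both vaccinations, 40/40/10% gives 0.0 (-7.2 to 7.2) and -30.0 (-36.0 to -23.9).

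In the first two scenarios the row shows no difference while PPSV23 is clearly more reactogenic than saline. In the third the sign reverses.

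**The case against.** The strongest reply is that the later document already has the vaccination right. SAP version 2 postdates the protocol, and SAP 3.2.1 and 6.2.1 use PPSV23 or saline after the second injection. Protocol section 9 lets the SAP modify non-primary analyses. The objective is descriptive and its estimand is a percentage per group, so no between-group difference is strictly required, and a reader can compare the planned per-group rates. On that view only a stale label remains. This stands as a limit on severity. It does not clear the point: the protocol promises a difference, and the visible SAP neither corrects it nor says that it was dropped.

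Other replies, and what is left of them:

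- **The subtraction is inferred.** True: unlike the Primary row, the Secondary row does not write it out. But the cross-time pair is the only pair it names.
- **The comparison may be deliberate.** It mirrors the immunogenicity comparison for the 7 additional serotypes, 20vPnC at Visit 2 against PPSV23 at Visit 3. That is plausible, and the documents do not settle it. If so, the row lacks an estimand and a label of its own.
- **Redaction.** Blacked-out SAP text may hold a Vaccination 2 difference, so its absence can be claimed only for the visible text. SAP 5.2.1 names the method in general terms.
- **The preferred contrast is also conditional.** Both groups at Vaccination 2 consist of people who went on to a second injection after different first vaccines, so it is not a pure randomised comparison, and Protocol 7.1 calls definitive discontinuation rare. This is correct. The Vaccination 2 contrast still applies the same rule to both groups at the same time and keeps saline.
- **The rates are assumed.** Also correct. They show possible size and are not a forecast.

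**Conclusion.** The mismatch is real. As written, the Secondary row of Protocol 9.4.2 attaches its difference to a pair of vaccinations that the secondary safety estimand does not contain, and it leaves out the saline control. The error in the difference equals the 20vPnC rate at Vaccination 1 minus the saline rate at Vaccination 2. Under the assumed rates that is roughly 15 to 50 points, and it would be zero if the two rates were equal.

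The consequence is contained. Rates for PPSV23 and saline after Vaccination 2 are planned separately, the endpoint is descriptive, and no hypothesis test, error rate, sample size or primary conclusion depends on it. It should be corrected before analysis. Confidence is high that the passages conflict; whether the cause is a labelling slip or an unlabelled supplementary comparison cannot be told from the documents.

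**What to change.** 1. In the Secondary row of Protocol 9.4.2, replace the pair with 20vPnC/saline [Vaccination 2] and 13vPnC/PPSV23 [Vaccination 2].
2. In SAP 6.2.1.1 and 6.2.1.2, state the between-group difference at Vaccination 2, 20vPnC/saline minus 13vPnC/PPSV23, with the Miettinen-Nurminen 95% interval. Apply it to local reactions over 10 days and systemic events over 7 days, in Japan-site participants with diary data after Vaccination 2. If redacted text already does this, only the protocol row needs changing.
3. If 20vPnC dose 1 against PPSV23 dose 2 was wanted, keep it as a separately labelled, non-concurrent descriptive comparison with its own estimand.

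The cost is one label and one table column. The diary data are already collected. Because the endpoint is not primary, Protocol section 9 allows the SAP to carry the correction.

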### 9.5. Interim Analyses

No interim analysis is planned in this study. Statistical analyses will be carried out when the final data for the specified analyses are available.

## **10. SUPPORTING DOCUMENTATION AND OPERATIONAL CONSIDERATIONS**

### **10.1. Appendix 1: Regulatory, Ethical, and Study Oversight Considerations**

#### **10.1.1. Regulatory and Ethical Considerations**

This study will be conducted in accordance with the protocol and with the following:

- Consensus ethical principles derived from international guidelines including the Declaration of Helsinki and CIOMS International Ethical Guidelines;
- Applicable ICH GCP guidelines;
- Applicable laws and regulations, including applicable privacy laws.

The protocol, protocol amendments, ICD, SRSD(s), and other relevant documents (eg, advertisements) must be reviewed and approved by the sponsor and submitted to an IRB/EC by the investigator and reviewed and approved by the IRB/EC before the study is initiated.

Any amendments to the protocol will require IRB/EC approval before implementation of changes made to the study design, except for changes necessary to eliminate an immediate hazard to study participants.

The investigator will be responsible for the following:

- Providing written summaries of the status of the study to the IRB/EC annually or more frequently in accordance with the requirements, policies, and procedures established by the IRB/EC;
- Notifying the IRB/EC of SAEs or other significant safety findings as required by IRB/EC procedures;
- Providing oversight of the conduct of the study at the site and adherence to requirements of 21 CFR, ICH guidelines, the IRB/EC, European regulation 536/2014 for clinical studies (if applicable), and all other applicable local regulations.

